5.3 VITAL SIGNS

5.3.1 Available data

Body temperature, pulse rate, respiratory rate, and blood pressure are recorded. Blood pressure and pulse are assessed with the participant rested.

For each vital sign record, assessment date, parameter name, test result and unit are collected.

5.3.2 Derivation rules

Abnormalities are defined in Table 6 below.

Table 6: Criteria to define vital signs abnormalities

	Pulse rate (bpm)	SBP (mmHg)	DBP (mmHg)	Temperature (°C)
Low	<50	<90	<45	<35.8
Normal	50-100	90-140	45-90	35.8-37.5
High	>100	>140	>90	>37.5

Note: For the worst-case analysis visit, as defined in section 2.2.5, an additional category low + high is defined if there are both low and high postbaseline values.

BMI (kg/m^2) will be derived as $= (\text{body weight (kg)}) / (\text{height at screening (m)})^2$ in function of C-GTI derivations.

5.3.3 Presentation of results

The SAF analysis set will be used for the evaluation of vital signs. For tables by analysis visit, only the baseline and last assessment analysis visits will be shown. Cross-tabulations will also include the worst-case analysis visit. All other analysis visits will be included in listings.

Vital signs parameters will be summarized using descriptive statistics at each analysis visit of interest. Actual values and changes from study baseline will be shown in the same table.

Abnormalities will be presented as cross-tabulations of the abnormality at each postbaseline analysis visit of interest versus the study baseline abnormality. The number of participants with treatment-emergent abnormalities will also be shown.

	Statistical Analysis Plan	
ARGX-113-2010	Final analysis	Final 1.0 of 29APR2025

The denominator for the percentage is the total number of participants with nonmissing data for the parameter and analysis visit in the SAF analysis set.

All vital signs data will be listed for the ROL analysis set, but only for participants with any postbaseline abnormality.

5.4 ELECTROCARDIOGRAMS

5.4.1 Available data

At a minimum, interval data (PR, QT, QTcF, QTcB and QRS intervals); ventricular rate; and overall interpretation will be recorded for each ECG. For each ECG record, parameter name, test result and unit, assessment date(time) are collected.

5.4.2 Derivation rules

When the ECG assessment date/time is registered down to the level of seconds, the part in seconds will not be considered for analysis purposes (e.g. allocation to phases/(sub)periods).

Abnormalities for HR, QRS, and PR interval are defined in Table 7 below.

Table 7: ECG normal ranges

	Heart rate (bpm)	PR (ms)	QRS (ms)
Low	<50	<120	-
Normal	50-100	120-220	0-120
High	>100	>220	>120

Note: For the worst-case analysis visit, as defined in section 2.2.5, an additional category low + high is defined if there are both low and high postbaseline values.

For QTcB and QTcF interval (ms), the following categories are defined:

- Actual values:
 - ≤ 450 (normal)
 -]450; 480]
 -]480; 500]
 - > 500
- Changes from study baseline:
 - ≤ 30 (normal)
 -]30; 60]
 - > 60

Note: The worst-case, as defined in section 2.2.5, is the highest postbaseline value and associated change.

5.4.3 Presentation of results

The SAF analysis set will be used for the ECG evaluation. For tables by analysis visit, only the baseline and last assessment analysis visits will be shown. Tabulations of abnormalities will also include the worst-case analysis visit. All other analysis visits will be included in listings.

Uncorrected QT interval and RR interval will only be listed.

	Statistical Analysis Plan	
ARGX-113-2010	Final analysis	Final 1.0 of 29APR2025

Continuous ECG parameters will be summarized using descriptive statistics at each analysis visit of interest. Actual values and changes from study baseline will be shown in the same table.

Abnormalities of the actual values will be presented as cross-tabulations of the abnormality at each postbaseline analysis visit of interest versus the study baseline abnormality. Numbers and cumulative numbers over decreasing abnormalities (QTcF and QTcB only) of participants with treatment-emergent abnormalities will also be shown. The denominator for the percentage is the total number of participants with nonmissing data for the parameter and analysis visit in the SAF analysis set.

Abnormalities of the QTcB and QTcF changes from study baseline will be presented as tabulations of the change abnormality at each postbaseline analysis visit of interest. Cumulative numbers over decreasing change from baseline abnormalities of participants with change abnormalities will also be shown. The denominator for the percentage is the total number of participants with nonmissing data for the parameter and analysis visit in the SAF analysis set.

All ECG data will be listed for the ROL analysis set, but only for participants with any postbaseline abnormality or change.

	Statistical Analysis Plan	
ARGX-113-2010	Final analysis	Final 1.0 of 29APR2025

6. VERSION HISTORY

This SAP for study ARGX-113-2010 is based on the protocol version 4.0, dated 02 May 2024.

6.1 CHANGES NOT COVERED BY PROTOCOL AMENDMENTS BEFORE DATABASE LOCK

6.2 CHANGES NOT COVERED BY PROTOCOL AMENDMENTS AFTER DATABASE LOCK

6.3 CHANGES TO THE FINAL STATISTICAL ANALYSIS PLAN

	Statistical Analysis Plan	
ARGX-113-2010	Final analysis	Final 1.0 of 29APR2025

8. LIST OF TABLES AND LISTINGS

8.1 TABLES

The mock ID refers to the table ID in the argenx mock library.

Table number	Title	PAS / DPS	Mock ID
14.1 DEMOGRAPHIC DATA			
GENERAL CHARACTERISTICS (14.1.X)			
14.1.1.1	Participant Analysis Sets and Number of Treatment Periods	ROL	DST01
14.1.1.2	Analysis Phase Duration	ROL	DST05
14.1.1.3	Analysis Period and Subperiod Duration	SAF	DST05
14.1.1.4	Treatment Discontinuation	SAF	DST03
14.1.1.5	Study Discontinuation	ROL	DST04
14.1.1.6	Protocol Deviations	ROL	DVT01
14.1.2.1	Demographic Data	ROL	DMT01
14.1.2.2	Baseline Disease Characteristics	ROL	DMT01
14.1.2.3	Concomitant Therapies by ATC Class (Level 1 and 3) and Generic Term	ROL	CMT01
14.1.2.4	Concomitant OCS Therapies by ATC Class (Level 1 and 3) and Generic Term	ROL	CMT01
14.1.2.5	Concomitant TCS Therapies by ATC Class (Level 1 and 3) and Generic Term	ROL	CMT01
14.1.2.6	Concomitant Rescue Therapies by ATC Class (Level 1 and 3) and Generic Term	ROL	CMT01
14.1.2.7	IMP Administration	SAF	EXT01

Statistical Analysis Plan

ARGX-113-2010

Final analysis

Final 1.0 of 29APR2025

14.2 EFFICACY DATA

EFFICACY (14.2.1.X)

14.2.1.1	CRoff: Proportion of Participants Who Achieved CRoff	SAF	EFT07b
14.2.1.2	CR/PROff: Proportion of Participants Who Achieved PR/CRoff	SAF	EFT07b
14.2.1.3	CRmin: Proportion of Participants Who Achieved CRmin	SAF	EFT07b
14.2.1.4	CRoff Without IMP: Proportion of Participants Who Achieved CRoff Without IMP	ROL	EFT07b
14.2.1.5	CR/PROff Without IMP: Proportion of Participants Who Achieved CR/PROff Without IMP	ROL	EFT07b
14.2.1.6	Sustained Remission: Kaplan-Meier Estimates of Duration of Sustained Remission	SAF	EFT09a
14.2.1.7	Relapse: Proportion of Participants with Relapse	ROL	EFT07b
14.2.1.8	Relapse: Kaplan-Meier Estimates of Time to Relapse	ROL	EFT09a
14.2.1.9	Relapse: Frequency Tabulation of Severity of Relapse	ROL	EFT07a
14.2.1.10	BPDAI: Descriptive Statistics of Actual Values, Changes From Baseline, and Percent Changes From Baseline in BPDAI Activity Score over Time	ROL	PDT01
14.2.1.11	BPDAI: Descriptive Statistics of Actual Values, Changes From Baseline, and Percent Changes From Baseline in BPDAI Total Score over Time	ROL	PDT01
14.2.1.12	IGA-BP: Frequency Tabulation of IGA-BP Score Over Time	ROL	EFT07d
14.2.1.13	Itch NRS: Descriptive Statistics of Actual Values and Changes From Baseline in Itch NRS 24-hour Average Score over Time	ROL	EFT03a
14.2.1.14	Itch NRS: Descriptive Statistics of Actual Values and Changes From Baseline in Itch NRS 24-hour Worst Score over Time	ROL	EFT03a
14.2.1.15	Treatment Failure: Proportion of Participants with Treatment Failure	ROL	EFT07b
14.2.1.16	C-GTI: Descriptive Statistics of CWS and AIS over Time	ROL	EFT03a
14.2.1.17	ABQOL: Frequency Tabulation of ABQOL 17 Items Over Time	ROL	EFT07d

	Statistical Analysis Plan	
ARGX-113-2010	Final analysis	Final 1.0 of 29APR2025

14.2.1.18	ABQOL: Descriptive Statistics of Actual Values and Changes From Baseline in ABQOL Total Score over Time	ROL	EFT03a
14.2.1.19	EQ-5D-5L: Frequency Tabulation of EQ-5D-5L 5 Dimensions Over Time	ROL	EFT07d
14.2.1.20	EQ-5D-5L: Descriptive Statistics of Actual Values and Changes From Baseline in EQ-5D-5L VAS Score over Time	ROL	EFT03a
14.2.1.21	DLQI: Frequency Tabulation of DLQI 10 Items Over Time	ROL	EFT07d
14.2.1.22	DLQI: Descriptive Statistics of Actual Values and Changes From Baseline in DLQI Score over Time	ROL	EFT03a
PHARMACODYNAMICS (14.2.3.X)			
14.2.3.1	Descriptive Statistics of Actual Values, Changes From Treatment-Period Baseline, and Percent Changes From Treatment-Period Baseline [REDACTED] over Time	SAF	PDT01
14.2.3.2	Descriptive Statistics of Actual Values, Changes From Treatment-Period Baseline, and Percent Changes From Treatment-Period Baseline in Anti-BP180 and Anti-BP230 Antibodies over Time	SAF	PDT01
IMMUNOGENICITY (14.2.4.X)			
14.2.4.1	Number and Percentage of Participants With Anti-drug Antibodies Against Efgartigimod over Time by Anti-drug Antibodies Against Efgartigimod Participant Classification	SAF	IMT01a
14.2.4.2	Prevalence and Incidence of Anti-drug Antibodies Against Efgartigimod	SAF	IMT02a
14.2.4.3	Descriptive Statistics of Anti-drug Antibodies Against Efgartigimod Titer Values over Time by Anti-drug Antibodies Against Efgartigimod Participant Classification	SAF	IMT03
14.2.4.4	Number and Percentage of Participants With Neutralizing Antibodies Against Efgartigimod over Time by Neutralizing Antibodies Against Efgartigimod Participant Classification	SAF	IMT01b
14.2.4.5	Prevalence and Incidence of Neutralizing Antibodies Against Efgartigimod	SAF	IMT02b
14.2.4.6	Number and Percentage of Neutralizing Antibodies Against Efgartigimod Positive Participants by Overall Anti-drug Antibodies Against Efgartigimod Participant Classification	SAF	IMT04

	Statistical Analysis Plan	
ARGX-113-2010	Final analysis	Final 1.0 of 29APR2025

14.3 SAFETY DATA

14.3.1 DISPLAYS OF ADVERSE EVENTS (14.3.1.X)

14.3.1.1	Treatment-Emergent Adverse Events Overview	SAF	AET01a
14.3.1.2	Overall Adverse Events Overview	ROL	AET01a
14.3.1.3	Treatment-Emergent Adverse Events by MedDRA System Organ Class and Preferred Term	SAF	AET02b
14.3.1.4	Overall Adverse Events by MedDRA System Organ Class and Preferred Term	ROL	AET02b
14.3.1.5	Treatment-Related Treatment-Emergent Adverse Events by MedDRA System Organ Class and Preferred Term	SAF	AET02b
14.3.1.6	Serious Treatment-Emergent Adverse Events by MedDRA System Organ Class and Preferred Term	SAF	AET02b
14.3.1.7	Serious Treatment-Related Treatment-Emergent Adverse Events by MedDRA System Organ Class and Preferred Term	SAF	AET02b
14.3.1.8	Serious Prednisone-Related Treatment-Emergent Adverse Events by MedDRA System Organ Class and Preferred Term	SAF	AET02b
14.3.1.9	Grade 3 or More Treatment-Emergent Adverse Events by MedDRA System Organ Class and Preferred Term	SAF	AET02b
14.3.1.10	Treatment-Related Grade 3 or More Treatment-Emergent Adverse Events by MedDRA System Organ Class and Preferred Term	SAF	AET02b
14.3.1.11	Prednisone-Related Treatment-Emergent Adverse Events by MedDRA System Organ Class and Preferred Term	SAF	AET02b
14.3.1.12	Procedure-Related Treatment-Emergent Adverse Events by MedDRA System Organ Class and Preferred Term	SAF	AET02b
14.3.1.13	Treatment-Emergent Adverse Events Leading to IMP Discontinuation by MedDRA System Organ Class and Preferred Term	SAF	AET02b
14.3.1.14	Treatment-Emergent Adverse Events of Special Interest by MedDRA System Organ Class and Preferred Term	SAF	AET02b

	Statistical Analysis Plan	
ARGX-113-2010	Final analysis	Final 1.0 of 29APR2025

14.3.1.15	Treatment-Related Treatment-Emergent Adverse Events of Special Interest by MedDRA System Organ Class and Preferred Term	SAF	AET02b
14.3.1.16	Treatment-Emergent Injection-Related Reactions by MedDRA System Organ Class and Preferred Term	SAF	AET02b
14.3.1.17	Serious Treatment-Emergent Injection-Related Reactions by MedDRA System Organ Class and Preferred Term	SAF	AET02b
14.3.1.18	Treatment-Emergent Adverse Events Overview for Injection Site Reactions	SAF	AET01c
14.3.1.19	Treatment-Emergent Injection Site Reactions by MedDRA System Organ Class and Preferred Term	SAF	AET02b
14.3.1.20	Fatal Treatment-Emergent Adverse Events by MedDRA System Organ Class and Preferred Term	SAF	AET02b
14.3.1.21	Common Treatment-Emergent Adverse Events by MedDRA System Organ Class and Preferred Term	SAF	AET02b

14.3.4 ABNORMAL LABORATORY VALUE LISTING (EACH PARTICIPANT)

LABORATORY DATA (14.3.4.1.X)

14.3.4.1.1	Descriptive Statistics of Laboratory Test Actual Values and Changes From Baseline Over Time	SAF	SFT01
14.3.4.1.2	Cross-Tabulation of Laboratory Abnormalities Versus Baseline Over Time	SAF	SFT02
14.3.4.1.3	Cross-Tabulation of Laboratory Toxicity Grades Versus Baseline Over Time	SAF	SFT03

VITAL SIGNS (14.3.4.2.X)

14.3.4.2.1	Descriptive Statistics of Vital Signs Actual Values and Changes From Baseline Over Time	SAF	SFT01
14.3.4.2.2	Cross-Tabulation of Vital Signs Abnormalities Versus Baseline Over Time	SAF	SFT02

ECG (14.3.4.3.X)

14.3.4.3.1	Descriptive Statistics of ECG Actual Values and Changes From Baseline Over Time	SAF	SFT01
14.3.4.3.2	Cross-Tabulation of ECG Abnormalities Versus Baseline Over Time	SAF	SFT02
14.3.4.3.3	Cross-Tabulation of QTcB and QTcF Abnormalities Versus Baseline Over Time	SAF	SFT03
14.3.4.3.4	Tabulation of QTcB and QTcF Change Abnormalities Over Time	SAF	SFT04

	Statistical Analysis Plan	
ARGX-113-2010	Final analysis	Final 1.0 of 29APR2025

8.2 LISTINGS

Listing number	Title	PAS / DPS
16.2.1 DISCONTINUED PARTICIPANTS		
16.2.1.1	Participant Analysis Sets	ROL
16.2.1.2	Treatment and Study Discontinuation	ROL
16.2.1.3	Study Visits	ROL
16.2.2 PROTOCOL DEVIATIONS		
16.2.2.1	Protocol Deviations	ROL
16.2.4 DEMOGRAPHIC DATA		
16.2.4.1	Demographic Data	ROL
16.2.4.2	Baseline Disease Characteristics	ROL
16.2.4.3	Concomitant Therapies	ROL
16.2.4.4	Concomitant Procedures	ROL
16.2.5 COMPLIANCE AND/OR DRUG CONCENTRATION DATA (IF AVAILABLE)		
16.2.5.1	IMP Administration	SAF
16.2.5.2	OCS Administration	ROL
16.2.6 INDIVIDUAL EFFICACY RESPONSE DATA		
16.2.6.1	Disease Status	ROL
16.2.6.2	Duration of Sustained Remission, Time to Relapse and Severity of Relapse	ROL
16.2.6.3	Lesion Assessments	ROL

Statistical Analysis Plan

ARGX-113-2010

Final analysis

Final 1.0 of 29APR2025

16.2.6.4	BPDAI	ROL
16.2.6.5	IGA-BP	ROL
16.2.6.6	Itch NRS	ROL
16.2.6.7	C-GTI	ROL
16.2.6.8	GTI Specific List	ROL
16.2.6.9	ABQOL	ROL
16.2.6.10	EQ-5D-5L	ROL
16.2.6.11	DLQI	ROL
16.2.6.12	[REDACTED]	ROL
16.2.6.13	Anti-BP180 and Anti-BP230 Antibodies	ROL
16.2.6.14	Efgartigimod Anti-drug Antibodies and Neutralizing Antibodies	ROL
16.2.7 ADVERSE EVENTS LISTINGS		
16.2.7.1	Adverse Events	ROL
16.2.7.2	Serious Adverse Events	ROL
16.2.7.3	Fatal Adverse Events	ROL
16.2.7.4	Treatment-Emergent Adverse Events Leading to IMP Discontinuation	SAF
16.2.7.5	Adverse Events of Special Interest	ROL
16.2.7.6	Adverse Events: Coding Information	ROL
16.2.8 LISTING OF INDIVIDUAL LABORATORY MEASUREMENTS BY PARTICIPANT, WHEN REQUIRED BY REGULATORY AUTHORITIES		
16.2.8.1	Laboratory Test Results for Participants with Post-Baseline Abnormal Values or Toxicities	ROL
16.2.8.2	Vital Signs Results for Participants with Post-Baseline Abnormal Values	ROL
16.2.8.3	ECG Results for Participants with Post-Baseline Abnormal Values	ROL

	Statistical Analysis Plan	
ARGX-113-2010	Final analysis	Final 1.0 of 29APR2025

	Statistical Analysis Plan	
ARGX-113-2010	Final analysis	Final 1.0 of 29APR2025

9. APPENDICES

9.1 GTI: DERIVATION OF CWS AND AIS

9.1.1 Allocate weights

Weights per item are attributed as specified below. GTI at Wx is evaluated versus previous GTI assessment. The first time point is referred to as *start (or previous)* and the second time point within each comparison is referred to as *follow-up (or current)*.

Increase, decrease or no change in medication intake compared to previous assessment are checked in the GTI assessment. A missing evaluation, including for external data, will be considered as no change with weight=0.

External GTI data (i.e., LDL/HbA1c/BP and BMI) are allocated to a GTI assessment based on dates. The last available value of these external data since previous GTI assessment will be used.

Changes from severe to moderate do not have any impact on calculation of CWS/AIS. Severe outcome on an item however is captured on the specific list (SL).

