1.3. Schedule of Activities

Table 1: Schedule of Activities for Participants Who Have Not Received Efgartigimod PH20 SC Since Baseline and Rolled Over Before Protocol Amendment 2 Is Effective

Study period	Baseline/ rollover (W0) ^{a,b}	Observation period								Follow-up period	Other visits		Applicable protocol section(s)
Study week(s)		W2	W4	W8	W16	W24	W32	W40	EoTP/W48	EoTP + 8 weeks	EDV ^c	UNS ^d	
Visit window		±2 d	±2 d	±7 d	±7 d	±7 d	±7 d	±7 d	±7 d	±3 d			
Eligibility (baseline only)													
Informed consent	X												Section 10.1.3
Eligibility check	X												Section 5.1 Section 5.2
Safety													
Physical examination (complete)	X								X		X		Section 8.3.1
Physical examination (brief)			X	X						X			Section 8.3.1
Weight	X					X			X		X	X	Section 8.3.1
Vital sign measurements	X	X	X	X	X	X	X	X	X	X	X	X	Section 8.3.1
ECG	X					X							Section 8.3.3
Urine pregnancy test ^e	X		X	X	Every 4 weeks				X		X		Section 8.3.5
Urinalysis	X	X	X	X		X		X	X	X	X	X	Table 7
Clinical chemistry and hematology	X	X	X	X	X	X	X	X	X	X	X	X	Table 7
GTI assessments (GTI-AIS, GTI-CWS, GTI-SL)	X					X			X		X		Section 8.3.6

Study period	Baseline/ rollover (W0) ^{a,b}	Observation period								Follow-up period	Other visits		Applicable protocol section(s)	
		W2	W4	W8	W16	W24	W32	W40	EoTP/W48	EoTP + 8 weeks	EDV ^c	UNS ^d		
		±2 d	±2 d	±7 d	±3 d									
Concomitant therapies/procedures	Continuous monitoring											Section 6.9		
AE monitoring	Continuous monitoring											Section 8.4		
Efficacy/disease monitoring														
Disease assessment ^b	X	X	X	X	X	X	X	X	X	X	X	X	X	Section 8.2.1.1
IGA-BP	X	X	X	X	X	X	X	X	X	X	X	X	X	Section 8.2.1.2
BPDAI	X	X	X	X	X	X	X	X	X	X	X	X	X	Section 8.2.1.3
Itch NRS	X	X	X	X	X	X	X	X	X	X	X	X	X	Section 8.2.1.4
Blood sample collection														
Immunogenicity	X		X	X	X	X	X	X	X	X	X	X	X	Section 8.9
PD (anti-BP180, anti-BP230 ^{(b) (4)})	X	X	X	X	X	X	X	X	X	X	X	X	X	Section 8.6
PK	X													NA
Substudy: vaccination antibody titers (serum)	Relative to the time of vaccination in ARGX-113-2009											Section 8.3.4.1		
Substudy: vaccination antibody titers (PBMCs)	Relative to the time of vaccination in ARGX-113-2009											Section 8.3.4.1		
Other														
Monitoring of concurrent BP therapy (Definitions of Terms)	X	X	X	X	X	X	X	X	X	X	X	X	X	Section 6.9 Section 8.2.1.1

Study period	Baseline/ rollover (W0) ^{a,b}	Observation period								Follow-up period	Other visits		Applicable protocol section(s)	

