- ^d A UNS may be performed if the participant has (or suspects they have) new BP lesions or other issues requiring site staff intervention, such as notable weight change. At these visits, the investigator will determine whether efgartigimod PH20 SC therapy must be started/resumed and will decide which assessments to conduct based on the purpose of the UNS. If relapse occurs, IGA-BP, BPDAI, and itch NRS assessments must be performed.
- ^e The urine pregnancy test is only applicable to WOCBP.

Table 2: Schedule of Activities for Participants Who Roll Over or Initiate Efgartigimod PH20 SC After Protocol Amendment 2 Is Effective, and Participants Who Stopped Receiving Efgartigimod PH20 SC After Roll Over but Before Protocol Amendment 2 Is Effective

Study period	Baseline/ rollover (W0) ^a	Day X ^b	Treatment period					Observation period ^c		Follow-up period		Other visits		Applicable protocol section(s)
			W1	W2	W4	W8	Every 4 W until EFG stop	Every 8 W after EFG stop	W48/ EoTP	F1 ^d	F2	EDV ^e	UNS ^f	
Study week(s)														
Visit timing (relative to day X, where applicable)		X	+1 W	+2 W	+4 W	+8 W	+ Every 4 W	+ Every 8 W	W48	EoTP +4 W	EoTP +8 W			
Visit windows			±2 d	±2 d	±2 d	±7 d	±7 d	±7 d	±7 d	±3 d	±3 d			
Eligibility (baseline only)														
Informed consent	X													Section 10.1.3
Eligibility check	X													Section 5.1 Section 5.2
Safety														
Physical examination (complete)	X	X ^g							X			X		Section 8.3.1
Physical examination (brief)						X	Every 16 weeks	Every 16 weeks ^{h,i}		X	X		X	Section 8.3.1
Weight ^j	X	X ^j		X ^j	X ^j	X	X ^j	X	X			X	X	Section 8.3.1
Vital sign measurements	X	X		X	X	X	X	X	X	X	X	X	X	Section 8.3.1
ECG	X						Week 24	Week 24 ⁱ	X			X		Section 8.3.3
Urine pregnancy test ^k	X	X			X	X	X	Every 4 weeks ^h	X	X	X	X		Section 8.3.5

Study period	Baseline/ rollover (W0) ^a	Day X ^b	Treatment period					Observation period ^c		Follow-up period		Other visits		Applicable protocol section(s)
Study week(s)			W1	W2	W4	W8	Every 4 W until EFG stop	Every 8 W after EFG stop	W48/ EoTP	F1 ^d	F2	EDV ^e	UNS ^f	
Visit timing (relative to day X, where applicable)		X	+1 W	+2 W	+4 W	+8 W	+ Every 4 W	+ Every 8 W	W48	EoTP +4 W	EoTP +8 W			
Visit windows			±2 d	±2 d	±2 d	±7 d	±7 d	±7 d	±7 d	±3 d	±3 d			
Urinalysis	X	X		X	X	X	X	X	X	X	X	X	X	Table 7
Clinical chemistry and hematology	X	X		X	X	X	X	X	X	X	X	X	X	Table 7
GTI assessments (GTI-AIS, GTI- CWS, GTI-SL)	X					X	Every 16 weeks	Every 16 weeks ^{h,i}	X			X		Section 8.3.6

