- ^e When a participant permanently discontinues IMP and/or is withdrawn from the study during the treatment period, study sites should attempt to perform the EDV within 7 days after the participant's final IMP administration and safety follow-up visits 4 and 8 weeks after the participant's final IMP administration. If a participant is withdrawn from the study during the observation period, refer to the SoA in [Table 1](#).
- ^f A UNS may be performed if the participant has (or suspects they have) new BP lesions or other issues requiring site staff intervention, such as notable weight change. At these visits, the investigator will determine whether efgartigimod PH20 SC therapy must be started/resumed and will decide which assessments to conduct based on the purpose of the UNS. If relapse occurs, IGA-BP, BPDAl, and itch NRS assessments must be performed.
- ^g A brief physical examination should be performed instead of a complete examination if the participant had a complete physical examination ≤ 4 weeks before day X.
- ^h Brief physical examinations, GTI, and QoL will be assessed every 16 weeks relative to the last performed assessment. WOCBP will have urine pregnancy tests every 4 weeks relative to the last performed assessment.
- ⁱ If the time point of the assessment does not coincide with a planned on-site visit, the assessment should be performed at the next on-site visit.
- ^j Weight must be measured only if the participant is being administered OCS.
- ^k The urine pregnancy test is only applicable for WOCBP. The pregnancy test at the F2 visit is only applicable for participants on efgartigimod PH20 SC at EoTP/EDV.
- ^l Efgartigimod PH20 SC will be administered once weekly, [REDACTED] (on days 1 and 8 of treatment) and weekly maintenance doses of 1000 mg will be used. Refer to [Section 6.3](#) for more information and to [Section 6.5](#) for information about (self-)administration. Week 48 is the last time point that participants may receive doses of efgartigimod PH20 SC.
- ^m Participants and/or their caregivers will be invited to receive at least 1 refresher training course for efgartigimod PH20 SC (self-)administration. Training may continue or be repeated until the participant (or caregiver) is considered capable of performing the (self-)administration.

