8.3.2. Physical Examinations

- A complete physical examination will include, at a minimum, assessments of the musculoskeletal, gastrointestinal, pulmonary, cardiovascular, respiratory, and neurological systems and general appearance, skin, and lymph nodes. Height and weight will also be measured without shoes, attired in light clothing, and recorded using validated instruments.
- Brief physical examination will include assessments of gastrointestinal, pulmonary, cardiovascular, and respiratory systems and general appearance.

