2.3 IMPUTATION AND ROUNDING RULES

2.3.1 Missing values

No imputation will be done of missing values (i.e., observed cases analysis).

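### GTI body-mass domain: read literally, SAP 9.1.1 scores later BMI change as zero for participants on efgartigimod whose last weight before week 48 falls at or before about week 24

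*SAP*

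**What the plan says.** **Scoring.** SAP 9.1.1 sets the comparator: "GTI at Wx is evaluated versus previous GTI assessment". BMI is treated as external data and allocated by date: "The last available value of these external data since previous GTI assessment will be used". For gaps it says: "A missing evaluation, including for external data, will be considered as no change with weight=0". It does not say what the start BMI is when the previous GTI assessment has none. SAP 5.3.2 derives BMI from body weight and screening height, so no weight means no BMI. AIS and CWS add up the interval scores over all postbaseline time points (SAP 9.1.2) and are tabulated only at the last assessment (SAP 4.1.3).

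**Collection.** In Protocol 1.3, Table 2, GTI is due at baseline, week 8, every 16 weeks after that (weeks 24 and 40) and week 48. In the weight row, the column for 4-weekly visits on efgartigimod carries footnote j: "Weight must be measured only if the participant is being administered OCS". The cells for baseline, week 8, week 48, early discontinuation, unscheduled visits and the 8-weekly visits after efgartigimod has stopped carry no j, although the row label does. Protocol 8.3.2 includes weight in the complete physical examination ("Height and weight will also be measured without shoes, attired in light clothing, and recorded using validated instruments"), which is due at baseline, week 48 and early discontinuation, but not in the brief one.

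**The concern.** Whether weight is collected at two of the GTI visits depends on whether the participant still takes OCS, and the scoring rule turns a missing value into a finding of no change. The objective served by this endpoint is the effect of efgartigimod on long-term glucocorticoid toxicity. The protocol aims to start efgartigimod without OCS where disease permits (6.3) and to taper OCS rapidly (6.9.1), so the participants exposed to the gap are those the design hopes to produce. Vital signs and clinical chemistry at the same visits carry no OCS condition, so of the external GTI inputs (LDL, HbA1c, blood pressure, BMI) only BMI is affected. No count of missing GTI items is planned, so a reader of the single tabulated AIS and CWS could not see the loss.

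**Working it through.** The plan gives no figure to reproduce. The check applies its rules to the Table 2 schedule.

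**Inputs.** GTI at weeks 0, 8, 24, 40 and 48 relative to day X (Table 2). Weight at weeks 0, 8 and 48 for everyone, and at the other 4-weekly visits only up to the last visit on OCS. BMI weights from SAP 9.1.1.1: ±21 for a change of more than 2 but less than 5 units, ±36 for at least 5, otherwise 0. BMI that stays below 25 scores 0, and gains count only at or above 25.

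**Step 1: which GTI visits have a BMI?** Each GTI takes the last weight since the previous GTI.

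| Last weight before week 44 | BMI at week 24 | BMI at week 40 | Week 48, literal reading |
|---|---|---|---|
| Week 8 | none | none | 0, no comparator |
| Weeks 12 to 24 | yes | none | 0, no comparator |
| Weeks 28 to 40 | yes | yes | scored |

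A further weight at week 44 changes nothing: week 40 already has a BMI. In general, the final score is lost when no weight was taken in the GTI interval that ends at the preceding assessment.

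**Step 2: size.** Assumptions, not from the documents: baseline BMI 32, flat until the last on-OCS visit, then a fall of 3 or 6 units. Total BMI score through week 48:

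| Last on-OCS visit | Fall after it | SAP, literal | Start = last known BMI | Weighed at every visit |
|---|---|---|---|---|
| Week 8 or 12 | 3 units over 12 weeks | 0 | −21 | −21 |
| Week 8 or 12 | 6 units over 12 weeks | 0 | −36 | −36 |
| Week 28 | 3 units over 12 weeks | −21 | −21 | −21 |
| Week 28 | 6 units over 12 weeks | −36 | −36 | −36 |
| Week 8 | 3 units, linear to week 48 | 0 | −21 | 0 |
| Week 8 | 6 units, linear to week 48 | 0 | −36 | −42 |

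Gains give the same figures with the opposite sign.

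For the linear rows with complete weights, the interval changes are 3 × 16/40 = 1.2, 1.2 and 3 × 8/40 = 0.6 units, none above 2, so the score is 0. For 6 units they are 2.4, 2.4 and 1.2, so the score is −21 − 21 + 0 = −42.

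**Step 3: in kilograms**, at assumed heights of 1.60 and 1.80 m: 2 units are 2 × 1.60² = 5.1 kg and 2 × 1.80² = 6.5 kg; 5 units are 5 × 1.60² = 12.8 kg and 5 × 1.80² = 16.2 kg.

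**The case against.** **The allocation rule closes much of the gap.** A reader might infer that anyone off OCS after week 8 has no BMI at weeks 24 and 40, so that all weight change after steroid withdrawal is erased. The documents do not support that. A weight at week 12, 16 or 20 supplies week 24, and one at weeks 28 to 36 supplies week 40. Losing everything from week 8 to week 48 requires that no weight is taken between those visits. This objection stands and sets the limits of the point.

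**The week 48 zero is a reading.** The SAP is silent on a missing start value, and a programmer could reasonably use the last known BMI, which recovers the change. That is true, but the literal text leads to 0, and the choice should not be left to programming.

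**Others are not affected.** Table 1 schedules weight at every GTI visit without an OCS condition, and the off-efgartigimod cells in Table 2 carry no j. This stands, except that the j on the row label leaves those cells, and week 8, ambiguous. An unscheduled visit, for which notable weight change is a named reason, may also supply a weight, but it is optional.

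**No contradiction with SAP 2.3.1.** A reader might set the zero rule against the general statement "No imputation will be done of missing values (i.e., observed cases analysis". That is weak: 9.1.1 is an instrument-specific scoring rule, and the SAP makes other specific exceptions, such as the averaging of missing ABQOL items.

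**Not every lost change is due to missing weight.** Slow change can score 0 even with complete data, because each interval is scored on its own. BMI is one domain of an additional secondary endpoint, in a single-arm descriptive study without hypothesis tests. Both points stand and limit the weight of the finding.

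**Conclusion.** The point holds in a limited form. For participants on efgartigimod under Table 2 whose last weight before week 48 falls at or before about week 24, the literal SAP text counts no BMI change after that weight, although a week 48 weight and an earlier weight both exist. The uncounted amount is 21 points for a change above 2 units or 36 for at least 5 units, where the BMI 25 conditions are met. AIS can lose it in either direction; CWS can lose only worsening. The loss enters the one time point that is tabulated, and it depends on OCS status.

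This rests on the literal reading of a missing comparator, on week 8 weight being unconditional (if the row-label j governs that cell too, the gap is wider) and on no unscheduled weight. The weeks are relative to day X, while the end-of-treatment visit is fixed at 48 weeks from baseline, so the week 24 boundary shifts for late starters. The number of participants affected cannot be derived from the documents, and the point figures are what an affected participant can lose, not an expected average.

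**What to change.** **SAP 9.1.1.1, BMI domain only.** When the previous GTI assessment has no BMI, use the last non-missing earlier BMI as the start value. Score 0 for missingness only if no current or no earlier BMI exists. Report the number of GTI intervals with missing BMI beside AIS and CWS. This needs no new data: it is a wording and programming change to a SAP that is already Final 1.0, to be recorded in its version history.

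The rule should not be extended to every GTI item. Glucose, blood pressure and lipids pair a change in value with a change in medication since the previous assessment. A value change over two intervals would not match a medication answer that covers one.

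**Protocol Table 2, if visits remain.** Reconcile the weight row with the GTI row, including the j on the row label, so that weight is recorded for all participants at GTI visits. The burden is a weighing at visits already attended, but the change is a protocol amendment and needs ethics committee approval (Protocol 10.1.1).

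**Downside.** Some BMI comparisons will span more than one GTI interval and will not always match the score under complete weighing: in the linear examples above, −21 against 0 and −36 against −42. The count of missing intervals lets a reader judge how often that arises.
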